6.1.2 Minimal Residual Disease Testing

Outcomes for patients with MM have improved significantly over the past decade, with improvements in both progression-free survival and overall survival.⁴⁴ Many patients are now achieving a complete response to treatment, and consequently highly sensitive assays are needed for detection of minimal residual disease (MRD) in patients with MM.⁴⁴ Results of multicolour flow cytometry and deep-sequencing studies suggest that among patients achieving a complete response, MRD-negative status is associated with substantial improvements in progression-free, and overall survival.⁴⁴ MRD status seems, therefore, to be an important prognostic factor in patients with MM. The prognostic value of sequencing based MRD testing was demonstrated in a publication by Hiroyuki Takamatsu et al at the 57th Annual ASH Meeting, 2015.⁴⁵ One hundred and twenty-three Japanese patients with newly diagnosed MM who received various induction regimens prior to ASCT were retrospectively analyzed. All patients received ASCT and were followed between June 15, 2004 and April 25, 2015. All patients had achieved a partial response (PR) or better after ASCT. Analyzed samples included: (1) BM slides from 96 MM patients at diagnosis, (2) fresh/frozen BM cells from 27 MM patients at diagnosis, (3) autografts and/or (4) post-ASCT BM cells obtained at the time of best response based on serum and urine tests. IGH-based ASO-PCR was performed as described previously⁴⁶. NGS-based (Next Generation Sequencing-based) MRD assessment was performed using the immunosequencing platform (Adaptive Biotechnologies, South San Francisco, CA)⁴⁷. Patients whose autografts were negative by NGS-based MRD assessment (N=19) had 100% PFS and OS at 5 years post ASCT irrespective of whether or not they received post ASCT treatment. Conversely, post ASCT treatment had a significant effect on the outcome of patients whose autografts

were MRD positive by NGS. Specifically, the NGS-based MRD positive patients who received post ASCT treatment (N=45) had a significantly better PFS.

To be able to study the interaction between allogeneic vaccine and MRD negativity on outcomes in our study, we plan to incorporate NGS-based MRD testing for all patients at enrollment, six months, one year and annually thereafter.

6.2 Administration of Allogeneic Myeloma Vaccine or Placebo

Treatment will be administered on an outpatient basis. Reported adverse events and potential risks for allogeneic myeloma/K562/GM-CSF vaccine and lenalidomide, as well as appropriate dose modifications for lenalidomide, are described below. No dose modification exists for the allogeneic myeloma K562/GM-CSF vaccine. No investigational or commercial agents or therapies other than those described below may be administered with the intent to treat the patient's malignancy.

6.2.1 Administration Parameters

At time of enrollment all patients will be on a stable, standard dose of lenalidomide given on days 1 – 21 of a 28 day cycle.

The following parameters must be present for each dose of the vaccine to be administered:

- No systemic infections requiring treatment
- Hemoglobin > 8g/dL
- Platelets > 20,000
- ALT/AST < 3X upper limit of normal
- Patient must be receiving lenalidomide on the day of the vaccine
- Missed vaccine doses can be made up within 2 weeks of the missed dose, with a delay by an equal number of days for the next dose (and the remaining doses), for the first 4 vaccine doses (there will be a minimum of one month between doses).
- Vaccine doses that are missed beyond the 4th dose of vaccine, can be made up within 1 month of the original date of administration. Subsequent doses do not need to be delayed.

6.2.2 Vaccine Formulation

The cell lines used for the vaccine preparation were manufactured and released by the Cell Processing and Gene Therapy Facility, a cGMP compliant facility, at the Sidney Kimmel Comprehensive Cancer Center at Johns Hopkins.. The vaccine cells are irradiated prior to cryopreservation and stored frozen in the vapor phase of liquid nitrogen until the day of use. The details of production, irradiation, freezing, and preparation for administration have been discussed in detail in the Investigational New Drug (IND) submission. Equal numbers (5×10^7 each) of the myeloma cell lines H929 and U266 cells will be combined with the bystander cell line K562/GM-CSF (5×10^6) to prepare the vaccine. Vaccine cells frozen in an injectable formulation Pentaspan® (10% Pentastarch in 0.9% sodium chloride with 2% human serum albumin and 5% DMSO) will be thawed on the day of vaccination in a 37°C water bath, mixed, and then taken up into three labeled syringes prior to administration. The cells are kept at 2-8°C with gel packs until administration. Injections should be started within 60 minutes of the thaw. Myeloma vaccine placebo injections will be saline solutions and will be prepared by the CTL at Johns Hopkins SKCCC in accordance with standard policies in order to maintain blinding.

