1. PROTOCOL SYNOPSIS

PROTOCOL TITLE: A Randomized, Double-blind, Placebo-Controlled Phase II Trial of an Allogeneic Myeloma GM-CSF Vaccine With Lenalidomide in Multiple Myeloma Patients in Complete or Near Complete Remission	
PROTOCOL NUMBER:	JHU Protocol #: J16118 Celgene Tracking #: RV-CL-MM-PI-005749
DATE PROTOCOL FINAL:	June 16, 2020
STUDY DRUG:	Allogeneic myeloma GM-CSF vaccine, Revlimid ® (lenalidomide)
INDICATION:	Augmenting clinical response with vaccine plus lenalidomide
STUDY PHASE:	Randomized Phase II
BACKGROUND AND RATIONALE: This study seeks to determine whether addition of an allogeneic myeloma vaccine can augment clinical responses to lenalidomide in patients with near complete remission (nCR), complete remission (CR) leading to a significant improvement in progression-free survival.	

STUDY OBJECTIVES AND ENDPOINTS:**Primary:**

- To compare the 2-year progression free survival of patients with multiple myeloma in a complete remission (CR), or near complete remission (nCR), treated with lenalidomide plus an allogeneic myeloma vaccine in combination with lenalidomide (with or without Prevnar vaccine) or versus placebo in combination with lenalidomide (control arm).

Secondary:

- To compare the 2-year progression free survival for those treated with or without Prevnar in addition to an allogeneic myeloma vaccine and lenalidomide
- To determine the rate of conversion from near CR (immunofixation positive) to true CR (immunofixation negative)
- To determine the rate of conversion from MRD (Minimal Residual Disease) positive status to MRD negative status by NGS (next generation sequencing).
- Determine time to response
- Determine progression free survival at 3 and 5 years
- Determine the toxicity of the allogeneic myeloma vaccine in combination with lenalidomide
- Measure tumor specific immunity and correlate with systemic immunity

STUDY DESIGN:

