
Lenalidomide: Patients will continue on a stable dose of lenalidomide on days 1 – 21 of a 28 day cycle until progression
 
Allogeneic myeloma vaccine consisting of 3 cell lines:
 
H929 5×10^7 cells/ vaccine
 
U266 5×10^7 cells/ vaccine
 
K562/GM-CSF 5×10^6 cells/ vaccine
 
Prevnar-13 administered with each myeloma vaccine
	
Allogeneic myeloma vaccine consisting of 3 cell lines to be manufactured by Aduro Biotech, and dispensed by the Cell Therapy Lab (CTL) at Johns Hopkins Sidney Kimmel Comprehensive Cancer Center (SKCCC).
 
Myeloma vaccine placebo injections will be prepared by the CTL at Johns Hopkins SKCCC.
 
Prevnar, and Prevnar placebo, will be prepared by the Pharmacy and Investigational Drug Service (IDS) at the Johns Hopkins Hospital.
 
All placebo will be made with saline.
 
For study participants, lenalidomide will be administered as a commercial drug.

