2. SCHEDULE OF STUDY ASSESSMENTS*

Procedure	Screen/Baseline ⁹ (Cycle 1 D 1 (28 days before)	Cycle 1 D 14 (+/- 3 days)	Cycle 2 D 14(+/- 3 days)	Cycle 3 D 14(+/- 3 days)	Cycle 6 D 14(+/-3 days)	1 year (+/-7 days)/Off- Study	18 months (+/-7 days)/Off-Study	2 years (+/-7 days)/Off- Study	30 months (+/-7 days)/Off-Study	3 years (+/-7 days)/Off- Study
Informed Consent	X									
Eligibility	X									
Complete medical history	X									
Interval history and review of patient vaccine reaction diary ¹		X X X	X	X X	X X X	X	X	X X	X	X
Review of systems ¹	X	X X X	X X	X X	X X X	X X	X X	X X	X X	X
Confirm diagnosis and stage	X									
Performance Status (ECOG) ¹	X	X X X	X X	X X	X X X	X X	X X	X X	X X	X
Concomitant Therapy ¹	X	X X X	X X	X X	X X X	X X	X X	X X	X X	X
Myeloma Vaccine or placebo ²		X X X	X X	X X	X X X			X		X
Prevnar Vaccine or placebo ³		X X X	X X	X X	X X X			X		X
Research Blood ⁴	X				X X			X		X
Bone Marrow Aspiration & Biopsy ⁵	X				X X			X		X
Safety Assessments:										
Adverse event query	-	X X X	X X	X X	X X X	X X	X X	X X	X X	X
Physical Examination, vital signs, weight	X	X X X	X X	X X	X X X	X X	X X	X X	X X	X
CBC with differential	X	X X X	X X	X X	X X X	X X	X X	X X	X X	X
Comprehensive panel	X	X X X	X X	X X	X X X	X X	X X	X X	X X	X
Pregnancy Testing ^{6,7}	X ₆	X X X	X X	X X	X X X	X X	X X	X X	X X	X
Disease Measurements:										
Minimal Residual Disease (MRD) testing ⁸	X ₁₀				X X			X		X
Protein electrophoresis (serum and 24 hr urine) or M-spike quantification (serum and 24hr urine)	X	X X X	X X	X X	X X X	X X	X X	X X	X X	X
Free light chain assay	X	X X X	X X	X X	X X X	X X	X X	X X	X X	X
Quantitative Immunoglobulins	X	X X X	X X	X X	X X X	X X	X X	X X	X X	X
Immunofixation studies (serum and 24 hour urine)	X	X X X	X X	X X	X X X	X X	X X	X X	X X	X
Beta-2 microglobulin	X									
Assessment of response ¹	X	X X X	X X	X X	X X X	X X	X X	X X	X X	X

In addition to the regularly scheduled study visits, an unscheduled visit can occur at any time during the study. Investigators may also assess participants via telemedicine at any point the investigator, local health or government authorities and/or other Hopkins authorities deem it appropriate. In these cases, an assessment may not include a physical exam or samples collection. All efforts should be made to perform in person visits if possible. Source documents must be maintained for these remote visits and unscheduled

visits. The date for the visit and any data generated must be recorded on the appropriate CRF.

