6.2.4 Potential Vaccine Toxicities

Toxicities associated with the intravenous administration of Pentaspan® include circulatory overload, abnormalities of coagulation (prolonged prothrombin, partial thromboplastin and clotting times), and hypersensitivity reactions characterized by wheezing, urticaria, hypotension, and anaphylactic/anaphylactoid reactions. Additionally, patients who are allergic to corn can also develop hypersensitivity to Pentaspan®.

The experience with K562/GM-CSF to date has shown it to be safe and well tolerated ⁴⁸. Elevated levels of GM-CSF can be detected in the serum for 3-5 days post vaccination, and this is accompanied by a transient rise in the white blood cell, neutrophil, and absolute

eosinophil counts. Toxicity is generally limited to myalgias and grade 1-2 injection site erythema, induration, tenderness, and localized pruritus. Most patients experience local vaccine site reactions that last for approximately 1 week; induration has ranged from 0.5 cm to as great as 20 cm. In other trials of GM-CSF producing vaccines, systemic reactions have included fever, headache, rash, generalized pruritus, and malaise.

As with any vaccine, there is a possibility of a serious allergic reaction although to date this has not been observed with any of the GM-CSF based vaccines administered here at Johns Hopkins. As with any investigational drug, other adverse reactions may develop that have not yet been described.

There is a theoretical risk of autoimmune disease reactivation or development with GM-CSF producing vaccines. In a previous multiple myeloma vaccine trial, induction of immune responses to autologous tumor cells has been demonstrated in vitro. Importantly, all multiple myeloma patients who had undergone autologous stem-cell transplant followed by vaccination have had normal kinetics of engraftment. There has been no serological or clinical evidence of autoimmune disease to date arising in recipients of the K562/GM-CSF vaccine in the previous AML, CML and myelomatrials.

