6.3 PREVNAR-13®

Other names: Pneumococcal 13-Valent Conjugate Vaccine

Classification: Infectious vaccine

Supplier: Prevnar-13 will be purchased from Wyeth Pharmaceuticals.

Dosage:

Prevnar-13 will be administered at 0.5ml dose by intramuscular injection. This dose will thus contain serotypes 1, 3, 4, 5, 6A, 6B, 7F, 9V, 14, 18C, 19A, 19F, and 23F and approximately 20 μ g of CRM₁₉₇ carrier protein; and 0.125mg of aluminum phosphate.

Since the product is a suspension containing an adjuvant, shake vigorously immediately prior to use to obtain a uniform suspension in the vaccine container. The vaccine should not be used if it cannot be resuspended or if particulate matter or discoloration is found.

Storage:

Vaccine is to be stored refrigerated at 2°C to 8°C (36°F to 46°F). It should not be frozen.

Contraindications:

Hypersensitivity to any component of the vaccine, including diphtheria toxoid, is a contraindication to use of this vaccine.

Warnings:

Healthcare professionals should prescribe and/or administer this product with caution to patients with a possible history of latex sensitivity since the packaging contains dry natural rubber.

Precautions:

Prevnar® is for intramuscular use only. Prevnar SHOULD UNDER NO CIRCUMSTANCES BE ADMINISTERED INTRAVENOUSLY. The safety and immunogenicity for other routes of administration (e.g., subcutaneous) have not been evaluated.

64 LENALIDOMIDE:

[figure not shown]

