8 RESPONSE CRITERIA

Baseline tumor assessments must occur within \leq 28 days of initiation of the study as indicated in Section 2, Schedule of Study Assessments.

Measurements of anti-myeloma efficacy will occur prior to the initiation of each cycle of lenalidomide. Myeloma response assessments will be based on the International Uniform Criteria.⁵²

Patients with confirmed progressive disease will be eligible to cross over on to the vaccine arm based on clinical judgement, available response data, and the PI's discretion, or be removed from study treatment.

Research blood and marrow will be used to assess responses during the trial. This will likely include but are not limited to:

1. Tumor specific immunity
2. Assessment of myeloid derived suppressor cell (MDSC) numbers and function by flow cytometry and T cell proliferation assays.
3. Activation markers on T cells by flow cytometry
4. Clonogenic myeloma precursors by flow cytometry.
5. Minimal Residual Disease (MRD) testing

The major purpose of this study is to determine whether the addition of an allogeneic myeloma vaccine can augment clinical responses to Lenalidomide.

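### Saline placebo against a vaccine that gives most recipients local reactions: the blind is likely compromised in many patients, and neither the progression date nor the timing of disease tests is protected from that

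*Combined protocol and SAP*

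**What the plan says.** The synopsis title calls this "A Randomized, Double-blind, Placebo-Controlled Phase II Trial". Section 1 adds "All placebo will be made with saline", and Section 6.2.2 states "Myeloma vaccine placebo injections will be saline solutions and will be prepared by the CTL", under that laboratory's standard policies for keeping the blind. The active product is irradiated cells in a starch, albumin and DMSO vehicle, which the placebo does not contain.

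Section 6.2.4, on experience with K562/GM-CSF, says "Most patients experience local vaccine site reactions that last for approximately 1 week; induration has ranged from 0.5 cm" up to 20 cm. It also lists erythema, tenderness, itching and a transient rise in white cells, neutrophils and eosinophils. It gives no percentage, no per-injection rate and no rate for saline. Each vaccination is three intradermal injections (6.2.3), planned at months 1, 2, 3, 6, 12, 24 and 36 (6.1). Section 2 schedules "Interval history and review of patient vaccine reaction diary" at study visits.

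The safeguards described are preparation by the cell therapy laboratory, lot and dose records held there (6.2.3), placebo in the same limbs on the same schedule (Section 2, footnote 2), and a Prevnar placebo.

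Section 11.2 runs PFS from randomization to progression or death, and Appendix 3 holds the criteria. No section names who declares progression, provides a blinded or central reading, or plans a check of blinding.

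On frequency, Section 8 has efficacy measured before each lenalidomide cycle. The Section 2 table has cycles 1, 2, 3 and 6, then 1 year, 18 months, 2 years, 30 months and 3 years. Footnote 1 allows assessment of response on day 1 of each cycle as well, but it is not attached to the M-protein, free light chain or immunofixation rows. Unscheduled visits are open-ended, and telemedicine visits may go without samples.

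**The concern.** Vaccine against placebo is the primary contrast. An inert saline injection does not imitate a product that leaves most recipients with erythema and induration for about a week, and none of the listed safeguards hides a skin reaction. Patients, and staff who see injection sites or read the diary, can therefore form a fair idea of the assignment.

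Appendix 3 is mostly laboratory thresholds, which limits bias in reading a result. It does not fix when the test is done. If patients thought to be on placebo are tested more often, their progressions are dated earlier and PFS appears longer on vaccine. Because Sections 2 and 8 disagree on frequency, that difference could arise without anyone breaking the protocol.

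**Working it through.** **The plan's own figure.** Inputs from 11.1: 18 v 36 patients, medians 18 and 42.8 months, HR 0.4199, two-sided 10%, 24 months' accrual, 36 to 60 months' follow-up, 1% loss per year. With hazard l = ln 2/median and loss hazard e = -ln(0.99)/12, the event probability is the average over t from 36 to 60 of l/(l+e) × (1 - exp(-(l+e)t)). This gives 0.825 for control and 0.528 for vaccine.
- Events: 18 × 0.825 + 36 × 0.528 = 14.85 + 19.0 = 33.9.
- SE of log HR: √(1/14.85 + 1/19.0) = 0.346.
- Power: Φ(0.868/0.346 - 1.645) = Φ(0.86) = 80.5%.

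Simulated log-rank power is 80.6%. The stated 80% reproduces and is unaffected by this point.

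**What a reaction reveals.** The documents give no rates, so these are assumptions: 60-80% of vaccinated and 5-10% of saline patients react.

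| Assumed rates (vaccine / saline) | P(vaccine given reaction) | P(placebo given no reaction) | Correct guesses |
|---|---|---|---|
| 80% / 5% | 28.8/(28.8+0.9) = 97% | 17.1/(17.1+7.2) = 70% | (28.8+17.1)/54 = 85% |
| 60% / 10% | 21.6/(21.6+1.8) = 92% | 16.2/(16.2+14.4) = 53% | (21.6+16.2)/54 = 70% |

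Always guessing vaccine is right in 36/54 = 67%. A reaction is strong evidence of vaccine; its absence is much weaker evidence of placebo. If reactions were independent across injections, even 51% per dose would give 1 - 0.49⁴ = 94% of vaccinated patients a reaction by the fourth dose. At 5% per dose the saline figure would be 1 - 0.95⁴ = 19%.

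**Why test timing matters.** Progression is found on average half an interval late: about 3 months with 6-monthly tests, and about 0.46 months with tests every 28 days (0.92 months). Unequal use of the two schedules shifts dates by about 2.5 months, against an 18-month control median.

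**Size under no true effect.** Simulated trials used 18 v 36 patients, exponential PFS with median 18 months in both groups, and accrual, loss and test level as in 11.1. There were 4,000 to 6,000 trials per scenario. The table schedule is Section 2, with 6-monthly tests assumed after 36 months. The result is the chance of a significant log-rank test favouring vaccine (nominal 5%). Repeat runs differed by about one point.

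| Who is tested every cycle (the rest follow the table) | Favours vaccine |
|---|---|
| Nobody, or everybody | 5-6% |
| Half of non-reactors, 60/10 | about 8% |
| Half of non-reactors, 80/5 | about 9% |
| All non-reactors, 60/10 | 9-10% |
| All non-reactors, 80/5 | 12-13% |
| All true placebo patients, no vaccine patients | about 16% |

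The last row needs perfect knowledge of the arm and is an extreme bound. Allowing for simulation error, the middle rows span about 7-13%.

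**The case against.** The strongest reply is that progression rests mainly on M-protein, immunofixation, free light chain and marrow values, that response categories require two consecutive assessments, and that Section 8 already has measurement before every cycle. If Section 8 is followed in all arms, the inflation above disappears. That is correct, and it is why the schedule conflict matters: the Section 2 table permits something quite different, and the plan does not say which governs. The simulations show sensitivity; they do not predict that staff will behave this way.

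Several stronger readings are tempting, and the documents do not support them.
- **The blind fails after the first injection.** Most is not all; no first-dose or saline rate is given; and the text describes K562/GM-CSF experience, not measured rates for this product. On the assumed rates, no reaction leaves only a 53-70% chance of placebo.
- **Progression is called unblinded.** No section says who calls it or that this person sees injection sites. What can be said is that the call is not protected.
- **Cross-over biases PFS.** Under Section 8, patients are "eligible to cross over on to the vaccine arm based on clinical judgement, available response data, and the PI's discretion" only after confirmed progression, hence after the PFS event. Section 14 is written for control patients, so the arm must be known by its own wording, not through skin reactions.
- **The products look different.** For Prevnar, "Since the product is a suspension containing an adjuvant, shake vigorously immediately prior to use" hints at it, but appearance in the syringe is inferred. The laboratory's standard policies may already mask it, and preparation details are in the IND.
- **Lenalidomide changes favour one arm.** No direction of bias can be shown.

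**Conclusion.** The point holds in this form: the stated double blind is likely to be compromised in many patients, in an unknown share, and the plan leaves both the progression date and the timing of disease tests exposed to that. Under assumed reaction rates of 60-80% v 5-10% and no true effect, the chance of a significant result favouring vaccine moves from about 5-6% to about 7-13% if half or all non-reactors are tested every cycle while others follow the Section 2 table. About 16% is a bound. With one schedule kept in all arms there is no inflation from this route. The facts about saline, local reactions and missing safeguards come from the documents; the sizes rest on the assumed rates and testing behaviour. The change should be made, but the point does not invalidate the design or the sample size.

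**What to change.** 1. In 11.2, derive the primary PFS event and date by program. Apply Appendix 3 to the recorded M-protein, immunofixation, free light chain, marrow and imaging values, in a file without arm, adverse-event or diary data. State which Appendix 3 list (progressive disease, relapse from CR, relapse from MRD-negative CR) counts as the event. Keep investigator-called progression as a sensitivity analysis.
2. The derivation does not cure unequal test timing. Reconcile Section 2 and Section 8 into one disease-assessment schedule, identical in all arms. Add a sensitivity analysis that dates progression found at an unscheduled test to the next scheduled assessment in every arm.
3. Record the patient's and the investigator's guess of assignment at a fixed early visit (cycle 6, the fourth injection, would serve), before progression can colour it. Describe the blind in the report accordingly.

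Separately, the cross-over wording in Sections 8 and 14, and the passages on discretionary and toxicity-based lenalidomide changes (6.4.12, 6.4.14, 6.6), need to be reconciled with each other; no rule is proposed here.

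Cost: protocol and SAP wording, a derivation program and one CRF question. No additional patients or readers are needed. The number of laboratory draws depends on which schedule the sponsor keeps. The downside is that the derived date may differ from the clinical call in a few patients, which the sensitivity analysis will show.
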